20.4 SAMPLE SIZE CALCULATIONS

With a minimum of 1000 eyes, the two-sided 95% confidence interval for the proportion of eyes rated as having acceptable performance will extend within 1.4% from the observed proportion assuming an expected overall satisfactory proportion of 95%.

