8. STUDY POPULATION

All study subjects will be enrolled from the normal surgical cataract population at up to 50 sites in the United States. Up to 1100 subjects will be enrolled in the study to achieve 1000 evaluable subjects at 3 months. However, data will be collected only for eyes implanted with the study lens. This study will include only subjects undergoing primary cataract extraction and IOL implantation and who meet all the study enrollment criteria. All subjects who meet the criteria will be offered enrollment in the study. Enrollment criteria may not be waived by the investigator. Any questions regarding patient eligibility are to be discussed with JJSV prior to subject enrollment. Subjects will be enrolled at each site sequentially until the recruitment goals are met. Enrollment will be competitive across sites.

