9. INVESTIGATOR SELECTION

9.1 INVESTIGATOR QUALIFICATIONS

JJSV will select ophthalmic surgeons who have completed a residency in ophthalmology (or its documented equivalent) and are licensed to practice medicine and perform surgery at his/her investigative site. Each site will have one designated principal investigator; some sites may have additional sub-investigators performing surgery for study cases.

Investigators will be selected from surgeons who are experienced in small-incision, cataract extraction and toric IOL implantation in cataract patients. Surgeons are defined as professionals with experience in handling the surgical products and are familiar with the English language. All communication between the site and the sponsor will be in English. Additionally, surgeons should have established their personalized A-constant for the TECNIS® 1-Piece lens platform.

All sites will be required to have adequate staff support for reporting and patient follow-up, as well as the instrumentation necessary to conduct study testing.

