10. EXPERIMENTAL PLAN

10.1 OVERVIEW

This study will be conducted in accordance with U.S. Code of Federal Regulations, the Declaration of Helsinki, GCP, ISO 14155 and all other applicable laws and regulations. The study will not begin until IRB approvals have been obtained.

This study will be a prospective, multi-center, open-label, post-marketing clinical study at up to 50 sites in the United States. Up to 1100 subjects will be enrolled after informed consent is obtained with up to 1000 treated subjects. Subject qualifications will be assessed at the preoperative visit according to the enrollment criteria. A subject can have either one eye or both eyes enrolled for inclusion in the study. Each eye will be tracked through the preoperative and postoperative schedule individually but only counted as a single subject.

At study start (prior to first subject implantation), each surgeons' preferred toric IOL (monofocal and presbyopia-correcting) and their average implantation volumes on a monthly basis will be collected using the SPQ (**Attachment A**).

All subjects will be examined through 3-months postoperatively according to the visit schedule described in Section 10.2, Visit Schedule.

A chart summary of all examination procedures required at each study visit is provided in **Appendix A**. Key preoperative data include visual acuities, manifest refraction, keratometry, biometry, and other routine cataract evaluation examinations and response from the SPQ

(Attachment A) will be collected prior to the first subject's operative visit for each surgeon. The operative visit will include general operative information and responses from the SHQ **(Attachment B)**, which will be collected for each implanted eye.

Key postoperative data collection at the 1-week visit for each eye will include UCDVA, medical findings/complications and surgeon satisfaction with rotational stability of the study lens. The 3-month visit will include UCDVA, manifest refraction, BCDVA, keratometry, and surgeon feedback from the SSQ **(Attachment C)** for each eye.

After the final study visit (last subject's 3-month visit) for each surgeon at each study site, surgeon feedback from the SEQ **(Attachment D)** will also be collected.

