10.7 POSTOPERATIVE PROCEDURES

Postoperatively, subjects will be examined according to the schedule in Section 10.2, Visit Schedule. One or both implanted eyes will be examined at 1-week and 3-month visits.

The postoperative case report form will include the following information, although not all are required at every visit:

UNCORRECTED DISTANCE VISUAL ACUITY

Monocular UCDVA is to be measured using a standard Snellen convention.

MANIFEST REFRACTION AND BEST CORRECTED DISTANCE VISUAL ACUITY

Manifest refraction is to be performed per the site's usual technique. Monocular BCDVA is to be measured using a standard Snellen convention.

MEDICAL FINDINGS

At each postoperative visit presence or absence of any medical or lens findings, complications, or serious or device-related adverse events will be noted.

ND:YAG CAPSULOTOMY

If an Nd:YAG capsulotomy is necessary, it is recommended that the procedure be performed at least 1 week prior to a study visit.

KERATOMETRY AND REFRACTION

Corneal curvature and refraction are to be measured using the investigator's usual methods. It is recommended that the same methods be used for all study subjects at the site for the duration of the study.

SURGEON SATISFACTION QUESTIONNAIRE (SSQ)

This 3-item questionnaire is self-administered and should be completed by the surgeon. The purpose of this questionnaire is to collect surgeon satisfaction with the clinical outcomes (e.g., rotational stability, uncorrected distance visual acuity) of the eye(s) implanted with the study lens.

Surgeon satisfaction with rotational stability will be collected for each implanted eye using a single-item from the SSQ at the 1-week visit. At the 3-month visit, surgeon feedback from the 3-item SSQ will be collected for each implanted eye.

SURGEON EXPERIENCE QUESTIONNAIRE (SEQ)

The surgeon experience questionnaire is a 5-item questionnaire that evaluates the surgeons' overall experience with the study lens in comparison to their historical experience with their preferred toric IOL (monofocal and presbyopia-correcting). This questionnaire is self-administered and should be completed only once after the last follow-up study visit (last subject's 3-month visit) for the study.

MEDICATIONS

Postoperative ocular medications should be used as is customary for each investigator and recorded in the source document for each subject, as appropriate. Only medications required for treatment of an SAE will be recorded on the case report forms.

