20.1 ANALYSIS POPULATION

For the primary endpoint, the primary analysis population will be all eyes implanted with a toric IOL (model ZCU150 through ZCU600) and with available data at the 3-month visit. For other endpoints, all eyes implanted with a toric IOL model ZCU150 to ZCU600 and with available data at the key timepoint for that endpoint will be used. In addition, data for the primary endpoint will also be evaluated by IOL model for lower-cylinder IOLs (ZCU150), medium-cylinder IOLs (ZCU225 to ZCU375) and for extended higher-cylinder IOLs (ZCU450, ZCU525 and ZCU600). For the surgeon preference questionnaire (SPQ) and the surgeon experience questionnaire (SEQ), the analysis population will be surgeons responding to these questionnaires.

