20.2 PRIMARY ENDPOINT

The primary endpoint for this study is the response to a single-item evaluating the surgeon's rating of overall level of satisfaction with the clinical outcome for each eye from the SSQ. Surgeon satisfaction is defined as having a score of 4 (satisfied) or 5 (very satisfied). The frequency and proportion of eyes with a rating of 4 or 5 and the 95% confidence interval for this proportion will be reported. In addition, the frequency and proportion with each response will be tabulated for this item.

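### The 1.4-point precision in section 20.4 holds for independent eyes, and neither it nor the interval in section 20.2 allows for shared surgeons or fellow eyes

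*Combined protocol and SAP*

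**What the plan says.** Section 20.4 justifies the sample size by precision alone. With at least 1000 eyes and an expected satisfactory proportion of 95%, "the two-sided 95% confidence interval for the proportion of eyes rated as having acceptable performance will extend within 1.4% from the observed proportion". It mentions no design effect, intraclass correlation, number of surgeons or share of bilateral subjects.

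Section 20.2 defines the primary result: "The frequency and proportion of eyes with a rating of 4 or 5 and the 95% confidence interval for this proportion will be reported". It names no interval method. Section 20.1 pools the eyes: "the primary analysis population will be all eyes implanted with a toric IOL", provided 3-month data are available. Nothing in section 20 mentions correlation within surgeon, site or subject.

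The source of the data is set out elsewhere:

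- The surgeon completes the rating, eye by eye (section 10.7): "At the 3-month visit, surgeon feedback from the 3-item SSQ will be collected for each implanted eye".
- Subjects may contribute two eyes (section 10.1): "A subject can have either one eye or both eyes enrolled for inclusion in the study". That section's remark that a subject is counted once concerns counting and is not an analysis rule.
- There are up to 50 sites (synopsis), and "some sites may have additional sub-investigators performing surgery for study cases" (section 9.1). The total number of surgeons is not given.
- Volumes may be unequal (section 8): "Enrollment will be competitive across sites".
- The surgeons are chosen by the sponsor (section 9.1): "JJSV will select ophthalmic surgeons who have completed a residency in ophthalmology".

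**The concern.** The primary outcome is a personal judgement. Each surgeon applies his or her own threshold for being satisfied, to eyes on which that surgeon also operated. With 1000 eyes and at most 50 sites there are on average 20 or more eyes per site, so many ratings share a rater. Fellow eyes share a patient as well. A binomial interval that treats every eye as a separate draw then claims more information than the data hold.

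Two separate things are affected. One is the planning figure in 20.4, which is given without the assumption behind it. The other is the interval to be reported under 20.2, which is the only inferential output on the primary endpoint. A reader who carries the result over to other surgeons would take it as more precise than it is.

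**Working it through.** **Inputs from the documents.** n = 1000 eyes minimum, p = 0.95, two-sided 95% (20.4); up to 50 sites (synopsis); 1000 evaluable subjects planned at 3 months (section 8). **Assumed, because the documents do not give them:** intraclass correlation (ICC), number of surgeons, spread of volumes, bilateral share and within-subject correlation.

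**1. The plan's figure.** 1.96 × √(0.95 × 0.05/1000) = 1.351 points, which rounds to 1.4. The arithmetic in 20.4 is right for independent eyes.

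**2. Half-width allowing for surgeons.** Multiply the independent half-width by √DEFF, with DEFF = 1 + (m − 1) × ICC and m the mean number of eyes per surgeon. Example: 50 surgeons, 1000 eyes, m = 20, ICC 0.05 gives DEFF = 1.95 and 1.351 × √1.95 = 1.89.

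Half-width in points, 50 surgeons of equal volume:

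| Eyes | Independent | ICC 0.01 | ICC 0.02 | ICC 0.05 | ICC 0.10 |
|---|---|---|---|---|---|
| 1000 | 1.35 | 1.47 | 1.59 | 1.89 | 2.30 |
| 1500 | 1.10 | 1.25 | 1.39 | 1.73 | 2.18 |
| 2000 | 0.96 | 1.13 | 1.27 | 1.64 | 2.11 |

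With 100 surgeons and 1000 eyes, ICC 0.01 / 0.05 / 0.10 gives 1.41 / 1.63 / 1.86. For unequal volumes, DEFF = 1 + ((1 + CV²)m − 1) × ICC. With CV = 1, 50 surgeons and 1000 eyes this gives 1.59 / 2.32 / 2.99.

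**3. Where 1.4 stops holding.** Setting the half-width to 1.4 gives ICC = ((1.4/h)² − 1)/(m − 1), where h is the independent half-width. With 50 equal-volume surgeons this is about 0.004 at 1000 eyes, 0.02 at 1500 and 0.03 at 2000.

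**4. Coverage of an unadjusted (Wald) interval when the target extends beyond these surgeons.** Beta-binomial simulation, p = 0.95, 50 surgeons, 1000 eyes, ICC 0.01 / 0.05 / 0.10:

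- equal volumes: 92 / 83 / 73%
- very unequal (exponential) volumes: 89 / 75 / 62%

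More eyes do not cure this. At 1500 eyes and ICC 0.02 the correct half-width is 1.39, so the 1.4 in 20.4 still holds. The unadjusted interval would nevertheless show 1.10 and cover about 87%.

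**5. Coverage when only the participating surgeons are the target.** With one eye per subject, the unadjusted interval covers 94% to 96% in the same simulations. With half of 1000 subjects bilateral (1500 eyes) and within-subject correlation 0.3 / 0.5 / 0.8, it covers about 92–93 / 91–92 / 88–90%.

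**6. Pairing and the planning figure.** With 1000 subjects, a fraction f bilateral and within-subject correlation ρ, the half-width is 1.351 × √[(1 − f + 2f(1 + ρ))/(1 + f)²]. At f = 0.5 and ρ = 0.3 / 0.5 / 0.8 this is 1.21 / 1.27 / 1.37. The worst case, ρ = 1 and f = 1/3, is 1.351 × √1.125 = 1.43. So with the planned 1000 evaluable subjects, pairing alone hardly moves the 1.4.

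**7. Reach of a suitable interval.** A site-clustered interval on the logit scale with a t reference is asymmetric near 95%. In simulation with 50 equal clusters, 1000 eyes and ICC 0.01 / 0.05 / 0.10, its mean reach is about 1.7 / 2.3 / 2.9 points below the estimate and 1.3 / 1.6 / 1.9 above. At ICC 0 the lower arm is already about 1.6. The symmetric half-widths in step 2 therefore understate its lower side.

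**The case against.** The strongest reply is that this is a descriptive feedback study of surgeons the sponsor selected. The hypothesis is only that outcomes will satisfy the surgeons (section 3). On that reading the participating surgeons are the whole target, surgeon clustering is irrelevant, and an eye-level interval is about right apart from fellow eyes. This is a reasonable reading, but the documents never state it, and pairing still costs some coverage under it.

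The documents are also silent rather than wrong: 20.2 names no method, so an adjusted interval is not excluded. That stands. The point applies to the eye-level binomial interval, which is the one 20.4 assumes.

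Three stronger readings are tempting, and the documents do not support them:

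- A reader might infer that 1.4 points is unattainable. With no ICC given this cannot be shown, and the figure survives small correlations, more so if bilateral subjects bring the eye count well above 1000.
- A reader might infer that bilateral enrolment by itself breaks the 1.4. It does not with 1000 evaluable subjects. Material widening from pairing alone would need the 1000 eyes to come from far fewer subjects than planned.
- A reader might infer that the study could reach a wrong conclusion. There is no success threshold, test or comparator, and the point estimate is unaffected.

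**Conclusion.** The concern holds as an omission. The 1.4 in 20.4 is an independent-eyes figure that does not say so, and 20.2 specifies no interval that respects the way the ratings arise. The omission is certain; its size is conditional on assumed correlations, surgeon counts, volumes and bilateral share.

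For inference beyond the participating surgeons, the shortfall in coverage of an unadjusted interval ranges from slight (ICC 0.01) to serious (ICC 0.10). For the participating surgeons only, it is the modest loss due to pairing. The consequence is overstated precision on the primary result and nothing more: minor to moderate severity, worth correcting because the correction is cheap.

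**What to change.** First state whether the result is meant to apply beyond the participating surgeons. If it is, add to 20.2:

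> The 95% CI for the proportion of eyes rated 4 or 5 will be a cluster-robust interval on the logit scale, clustered on site (which contains surgeon and subject), with a small-sample-corrected variance and a t reference with sites minus 1 degrees of freedom. The same method will be used for any CI reported by cylinder group. If all eyes are rated 4 or 5, an exact CI will be reported and labelled unadjusted.

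If only the participating surgeons are meant, say so and cluster on subject instead; in the bilateral simulations that interval covers about 95% to 96%.

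Replace the statement in 20.4 with:

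> With 1000 eyes and an expected 95%, the half-width is about 1.4 points if eyes are independent. For assumed within-surgeon ICCs of 0.01, 0.05 and 0.10 with 50 surgeons of equal volume, the planned interval is expected to extend about 1.7, 2.3 and 2.9 points below and 1.3, 1.6 and 1.9 points above the observed proportion, and further if volumes are unequal or there are fewer sites.

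Add the same figures for the number of eyes actually expected.

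**Cost.** Some SAP wording and a few lines of code. No new data are needed: section 14.2 already gives each eye a site/ID number. The reported interval will be wider and the stated precision less favourable. In simulation, site clustering covers about 94% to 95% with equal clusters, about 92% to 94% with 50 very unequal ones, and about 90% to 93% with 25 single-surgeon sites of very unequal volume. In that last setting the unadjusted interval covers about 85 / 61 / 48% at ICC 0.01 / 0.05 / 0.10. Site clustering is conservative if the surgeons are treated as fixed, and it assumes that no surgeon operates at two study sites.

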20.5 INTERIM REPORTS

Interim study progress reports may be conducted during the study.

APPENDIX A: SUMMARY OF PROCEDURES REQUIRED AT EACH VISIT

Examination	Preop (Visit 1)	Op (Visit 2)	1-week (Visit 3)	3-month (Visit 4)
Informed consent, ocular history, enrollment criteria, IOL power calculations	+			
Biometry	+			
Keratometry	+			+
Lens power/serial number		+		
Surgeon Preference Questionnaire (SPQ)	+ ^a			
Surgical Handleability Questionnaire (SHQ)		+ ^b		
UCDVA	+		+	+
Manifest refraction	+			+
BCDVA	+			+
Medical findings/lens findings/complications/adverse events	+		+	+
Surgeon satisfaction with rotational lens stability (Single-item from SSQ)			+	
Surgeon Satisfaction Questionnaire (SSQ)				+
Surgeon Experience Questionnaire (SEQ)				+ ^c

^a At study start (prior to first subject implantation)^b At the operative visit for each implanted eye^c At the last subject's 3-month visit for each surgeon at each study site

APPENDIX B: ADVERSE EVENT AND COMPLAINT REPORTING INSTRUCTIONS

All adverse events and complaints related to using JJSV products must be reported to JJSV.

ALL ADVERSE EVENTS AND COMPLAINTS:

For events that are not considered serious or related to the study device:

1. Record the event and/or complaint on the case report form that corresponds to the visit during which awareness of the event occurred. Additionally, a complaint may be reported via a telephone call to JJSV.
2. Send the completed case report form to JJSV in a timely manner

SERIOUS ADVERSE EVENTS OR DEVICE DEFICIENCIES THAT MAY HAVE LED TO A SERIOUS EVENT

In the event of a serious event (i.e., life- or sight-threatening incident) whether or not related to the device, or a device deficiency that may have led to a serious event, the investigator shall:

1. Notify JJSV immediately (no more than 48 hours after learning of the event) as follows:
 - a. Contact the following JJSV personnel by phone and/or email:
 - b. Complete a Detailed Adverse Event Form and submit to JJSV

NON-SERIOUS, DEVICE-RELATED EVENTS:

For events that are not considered serious but are believed related to the study device (ADEs):

1. Complete a Detailed Adverse Event Form
2. Ensure the data are submitted to JJSV within a timely manner.

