11. ADVERSE EVENTS AND PRODUCT COMPLAINTS

11.1 ADVERSE EVENT DEFINITIONS

Adverse Event (AE)

An adverse event is defined (following ISO 14155) as any untoward medical occurrence, unintended disease or injury, or untoward clinical signs (including abnormal laboratory findings) in subjects, users or other persons, whether or not related to the study device.

Serious Adverse Event (SAE)

An adverse event is considered serious (following ISO 14155) if it is an untoward occurrence which may or may not be related to use of the study device that

- Is sight- or life-threatening,
- Results in death,
- Requires inpatient hospitalization or prolongation of hospitalization (a planned hospitalization for a pre-existing condition without a serious deterioration in health is not considered a serious adverse event),
- Results in permanent impairment of a body structure or body function,
- Necessitates medical or surgical intervention to prevent permanent impairment to a body structure or function, or,
- Results in fetal distress, fetal death or a congenital abnormality or birth defect

Device-Related Adverse Event/Adverse Device Effect (ADE)

A device-related adverse event is defined as any adverse event that is believed to be definitely, probably or possibly related to the study device (following the guidelines in Section 11.4, Causal Relationship). A device-related event is also considered an adverse device effect (ADE; following ISO 14155) resulting from the use of the study device that may result from user error, insufficiencies or inadequacies in the instructions for use, deployment, implantation, installation, operation or any malfunction of the device.

Study-Specific Serious Anticipated Adverse Events

The following is a list including, but not limited to, ocular serious adverse events that are anticipated and must be reported to JJSV for this study. Any events that are unlikely but anticipated (i.e., endophthalmitis or toxic anterior segment syndrome) will be reported to FDA and other appropriate regulatory agencies.

- Endophthalmitis/Intraocular infection
- Hypopyon
- Hyphema
- IOL dislocation

- Cystoid macular edema: Macular edema diagnosed by clinical examination and adjunct testing (e.g. OCT, FA) resulting in BCDVA of 20/40 or worse at 1 month or later
- Pupillary block
- Retinal detachment/tear
- Corneal edema
- Chronic iritis or uveitis
- Raised IOP that persists (i.e., is present at the last study visit)
- Toxic anterior segment syndrome (TASS)

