- Visual symptoms requiring secondary surgical intervention (e.g., lens removal)
- Tilt, decentration, IOL rotation requiring secondary surgical intervention (e.g., repositioning)
- Residual refractive error resulting in a secondary surgical intervention
- Retained lens material resulting in secondary surgical intervention

NOTE 1: *Wound burps during the first week postoperatively, suture removal, planned blepharoplasty and Nd:YAG capsulotomy (for PCO) are not considered adverse events for this study.*

NOTE 2: *Corneal edema, and chronic anterior uveitis/iritis will be considered serious if corneal edema resulting in BCDVA of 20/40 or worse at 1 month or later; and Grade 1+ uveitis/iritis persists for greater than 3 months after surgery). Raised IOP requiring treatment (Elevation of IOP \geq 10 mmHg above baseline to a minimum of 25 mmHg) will be considered serious if present at the last study visit.*

Unanticipated Adverse Device Effect (UADE)/Unanticipated Serious Adverse Device Effect (USADE)

Any USADE (ISO 14155) is defined as any serious adverse effect on health or safety or any life-threatening problem or death caused by, or associated with, a device, if that effect, problem, or death was not previously identified in nature, severity, or degree of incidence in the investigational plan (i.e., this protocol), application (including a supplementary plan or application), or risk assessment, or any other unanticipated serious problem associated with a device that relates to the rights, safety, or welfare of subjects.

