11.3 ADVERSE EVENT AND COMPLAINT REPORTING REQUIREMENTS

All adverse events and any complaint encountered using any JJSV product, regardless of severity and whether or not attributed to the study device(s), are to be reported to JJSV and recorded on the case report form corresponding to the visit during which awareness of the event occurred. Adverse events are also to be reported to the reviewing IRB as per their reporting requirements. If required, adverse events will be reported to the appropriate regulatory agencies (e.g., FDA) according to all applicable laws and regulations. Specific instructions on notification procedures to JJSV are included in Error! Reference source not found..

General guidelines are provided below:

Adverse Event Reporting

An adverse event that is not serious or device-related is to be reported to JJSV in a timely manner. Notification of non-serious and non-device-related adverse events will occur by submitting events on the CRF when noted. Such adverse events are also to be reported to the reviewing IRB per their reporting requirements.

Complaints/Device Deficiency Reporting

A general product complaint or device deficiency is to be reported to JJSV in a timely manner. Notification of complaints/device deficiencies will occur by either submitting complaints on the CRF when the complaint occurred (e.g., operative form) or by a phone call to the Sponsor. Any device deficiency that could have led to a serious adverse event without suitable action or intervention, or under less fortunate circumstances, must be reported to the sponsor immediately (no later than 24 hours after detection). Device deficiencies that could have led to a serious adverse event should also be reported to the investigator's IRB per their reporting requirements.

Serious and/or Device-Related Adverse Event Reporting

Serious and/or device-related events (ADEs) are to be documented using the SAE/ADE Detailed Page. In the event of a serious adverse event (SAE), which may or may not be related to use of the study device, JJSV must be notified immediately (no later than 48 hours after detection). Any SAE is to be reported by phone (and/or email) and by submitting a completed SAE/ADE Detailed Page. Any SAE or device-related AE should also be reported to the investigator's IRB per their reporting requirements.

Unanticipated Adverse Device Effect (UADE)/Unanticipated Serious Adverse Device Effect (USADE) Reporting

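### Appendix B describes a serious event more narrowly than Section 11.1, so a site sorting events by it could send listed SAEs such as lens repositioning to a route with no fixed deadline

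*Combined protocol and SAP*

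**What the plan says.** Section 11.1 makes an adverse event serious if it meets any one of six criteria. The first is "Is sight- or life-threatening". The others include "Results in death", "Requires inpatient hospitalization or prolongation of hospitalization" and "Necessitates medical or surgical intervention to prevent permanent impairment to a body structure or function"; the remaining two cover permanent impairment and fetal outcomes. The section then gives a non-exhaustive list of anticipated serious ocular events that sites must report to the sponsor. One entry is "Tilt, decentration, IOL rotation requiring secondary surgical intervention (e.g., repositioning". Note 2 states when corneal edema, chronic uveitis or iritis, and raised IOP count as serious.

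Section 11.3 sets the clock: for an SAE, whether or not device-related, "JJSV must be notified immediately (no later than 48 hours after detection". It sends the reader elsewhere for notification procedures, but the cross-reference prints as an error.

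Appendix B holds the site instructions and sorts events into three routes. The serious route opens with "In the event of a serious event (i.e., life- or sight-threatening incident) whether or not related to the device" and requires notice within 48 hours. For events that are not serious but are device-related, the site completes a detailed form and is told: "Ensure the data are submitted to JJSV within a timely manner". For events that are neither serious nor device-related, the site records the event on the visit's case report form and sends it in, again with no stated number of hours or days.

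**The concern.** The abbreviation in Appendix B's parenthesis introduces a restatement, not an example. Read literally, it replaces the Section 11.1 definition with the first criterion alone, on the page that tells a site which route to take. A site has reason to use that page. Its title says that it contains the reporting instructions, and it is the only text in the document that fits the pointer in Section 11.3.

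The events most exposed are closely tied to a toric lens. Section 7.1 says that the lens is designed to minimize large rotations, and Section 17 says that it is designed for better rotational stability than its predecessor. Surgery to reposition a rotated lens is therefore a safety signal that the sponsor would want early. It is a listed SAE under Section 11.1, yet it need not threaten life or sight.

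**Working it through.** No sample size, rate or error probability enters this point. The check is a comparison of the passages and a count.

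**Criteria.** Section 11.1 has six: threat to sight or life, death, hospitalization, permanent impairment, intervention to prevent permanent impairment, and fetal outcomes. Appendix B's parenthesis names the first, so 1 of 6.

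**Study-specific list.** Section 11.1 has 15 entries:
- Eleven are named conditions: endophthalmitis, hypopyon, hyphema, IOL dislocation, cystoid macular edema, pupillary block, retinal detachment or tear, corneal edema, chronic iritis or uveitis, persistent raised IOP, and toxic anterior segment syndrome.
- Four are defined by a secondary surgical intervention. The reasons are visual symptoms; tilt, decentration or rotation; residual refractive error; and retained lens material.

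So 11 + 4 = 15. Appendix B mentions none of them. Several of the eleven, such as endophthalmitis and retinal detachment, are plainly sight-threatening and would meet the parenthesis anyway. The four surgical entries need not be, so at least 4 of 15 are exposed.

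**One event followed through each reading.** Take an eye whose lens rotates and is surgically repositioned, with no threat to sight:

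| Reading | Time limit for notice | Detailed form | Medical monitor's stated review (15.3) |
|---|---|---|---|
| Sections 11.1 and 11.3 | 48 hours | Yes | Yes, as serious |
| Appendix B, taken as non-serious, judged device-related | None in hours or days | Yes | Yes, as device-related |
| Appendix B, taken as non-serious, judged unrelated | None in hours or days | No, visit form only | Not covered |

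The time limit is lost in both Appendix B readings. The detailed form and the stated monitor review are lost only in the last.

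**The case against.** The strongest answer is that Section 11.1 is the definitions section and Section 11.3 states the 48-hour rule for every SAE. Section 10.7 sends sites to Section 11 first. Appendix B's own heading for this route uses the term serious adverse events, and its other routes apply only to events not considered serious. Read with Section 11.1, repositioning belongs on the 48-hour route. Section 15.2 also provides training before any implant and monitoring visits that check reporting. All of this stands, and it limits the consequence: misrouting requires a site to follow the parenthesis over the body of the protocol, and nothing in the documents shows that sites do so. It does not remove the conflict, because Appendix B neither repeats the definition nor refers to it.

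The count of 1 in 6 also overstates the practical gap. A site would hardly leave a death off the urgent route, and fetal outcomes should be rare in a cataract population. The real gap is mainly the four surgical entries, plus hospitalization or impairment that does not threaten life or sight.

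A reader might go further and infer that SAE counts across up to 50 sites would mix two definitions. The documents do not show this. Appendix B governs how and when to notify, not how events are classified for analysis. Section 20.3 plans the proportion of eyes with findings or adverse events and specifies no separate SAE rate. Section 6.2, item 7, names secondary surgical interventions, so repositionings are to be counted whatever their seriousness label.

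A reader might also infer that the medical monitor would miss rotation cases altogether. Section 15.3 covers device-related events as well as serious ones, so a repositioning judged definitely, probably or possibly device-related stays within that review. Section 15.3 also sets no review time, so a delayed review cannot be measured against the plan.

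**Conclusion.** The conflict is real: Appendix B's wording of what triggers the 48-hour notice is narrower than Section 11.1 and inconsistent with Section 11.3. Its size is one of six criteria named, none of the 15 listed events mentioned, and at least four of those 15 exposed. For these four, a site sorting by Appendix B could move from a 48-hour limit to no fixed limit. For those also judged unrelated to the device, the detailed form and the monitor's stated review could be lost too.

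This rests on two assumptions: that the site relies on Appendix B over Sections 11.1 and 11.3, and that the event does not itself threaten life or sight. The documents give no rate for these events, so the number affected cannot be estimated. The events should still reach the sponsor, since Section 11.3 and Appendix B make all adverse events reportable. No planned estimate is shown to change. The matter is worth correcting as a safety-reporting inconsistency.

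**What to change.** In Appendix B, replace the parenthesis with a reference to any event that meets a seriousness criterion in Section 11.1 or is on its study-specific list, as qualified by Note 2. Repair the broken cross-references in Section 10.7 (adverse events paragraph) and Section 11.3 so that both point to Appendix B.

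The same Appendix B route gives 48 hours for device deficiencies that could have led to an SAE, while Section 11.3 gives 24. That is a separate mismatch, but the two figures should be reconciled in the same edit.

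The cost is one phrase, two cross-references, IRB approval of the amended text (Section 13.1) and a memo to sites. There may be a few more 48-hour reports, but Section 11.3 already requires them, so redefining the trigger adds no new duty.
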